### Data Sources

Four core data sources will be utilized as part of the study including the Pre-Treatment Survey and Post-Treatment Survey of patients and caregivers; provider post-interviews; EHR and Aria (Geisinger's radiation oncology software) data; FCA administrative metrics/analytics; and health system operational data. For example, GHS' Oncology Service Line collects symptom burden (patient-reported outcomes data using the MD Anderson Symptom Inventory) as standard clinical practice during active chemotherapy in the outpatient setting; these data are available in the EHR to evaluate as clinical indicators. Prior to baseline survey data collection, patient and caregiver questionnaires will be field tested for content validity (e.g., do the questions make sense, is anything duplicative or unclear, etc.). Feedback regarding completion time will be evaluated to reduce burden, a sensitive topic considering the clinical status of participants. Collectively, this feedback will be used to finalize the study tools included in surveys (e.g., study questionnaires). Any revisions made to the surveys as part of the field test will be submitted as an IRB amendment.

The data elements collected and used as part of the analysis purposes are as follows:

#### **I. Patient:**

- Study ID
- Patient Survey Responses
- Date of birth
- Date of death (where applicable)
- Gender

- Treatment Location (GMC, GWV, GCMC)
- Problem list diagnoses
- Outpatient Encounters
  - Date
  - Flag for interpreter used
    - # distinct specialties seen
  - Visit type
  - Provider ID
  - Provider type
  - Clinic/department/location/specialty
  - Diagnosis codes associated with visit (flag primary)
  - Disposition (completed/no-show/cancel)
- Inpatient Encounters
  - Admission date
  - Diagnosis codes associated with discharge (flag primary)
  - Location (e.g. ICU)
  - Discharge date
- ED encounter data
  - Date
  - Diagnoses associated with visit (flag primary)
  - Flag if resulted in an admission
  - MD Anderson Symptom Inventory
- FCA (Harmonized Care) Usage
  - Dates of log-on
  - All features accessed in the application including dates accessed and number of views
  - Interest and Information
    - Number of topics added
    - Number of events added
    - Number of photos added
  - Appointments
    - Number of calendars added
    - Number of appointments added
  - Care Partners
    - Number of care partners added
  - Medication Management
    - Number of medications scheduled
    - Number of questions added
  - Notes
    - Number of private notes
    - Number of shared notes
  - Profile

- Number of profile pictures added

## II. Caregiver:

- Study ID
- Caregiver Survey Responses
- Age
- Gender
- FCA (Harmonized Care) Usage
  - Dates of log-on
  - All features accessed in the application including dates accessed and number of views
  - Interest and Information
    - Number of topics added
    - Number of events added
    - Number of photos added
  - Appointments
    - Number of calendars added
    - Number of appointments added
  - Care Partners
    - Number of care partners added
  - Medication Management
    - Number of medications scheduled
    - Number of questions added
  - Notes
    - Number of private notes
    - Number of shared notes
  - Profile
    - Number of profile pictures added

## III. Non-Participants:

- Non-Participant Survey Responses

## IV. Providers:

- Study ID
- Provider Type (MD, PA, NP, etc)
- Practice Site (e.g Rad/Onc, Hem/Onc, etc.)
- Age
- Race/Ethnicity

- Gender
- Interview Responses
- FCA (Harmonized Care) Usage:
  - Opened Dashboard
  - Encounter Type
  - Medication Questions
    - Number of Responses
  - Calendars
    - Number of filters on calendars

#### **4.8.2 Statistical Power and Sample Size Considerations**

Power nor sample size was estimated for this exploratory evaluation study. Therefore, a sample size of 50 Case Dyads and 50 Control Dyads was selected to describe any differences in quality and performance metrics associated with FCA use. Any statistical tests are meant to be descriptive only.

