***Observe FCA in clinical oncology practice to evaluate quality and performance indicators.***

Integrate exposure to FCA as standard of care in a conveniently selected clinic for persons with lung cancer and their caregivers. Clinicians in this clinic have contributed to the development and testing of FCA as standard of care at Geisinger Medical Center in Danville, PA (“GMC”). This clinic will serve as the treatment site. Electronic health records and FCA dashboard analytics will be used to evaluate clinician use of the tool. Clinicians at the treatment site will provide interview data describing their experience related to quality, FCA adoption and implementation into workflow integration at the post-period;

### 3.2 Specific Aim 2

***Observe FCA use among patients and caregivers to evaluate quality and performance indicators associated with oncology care.*** From the treatment site, identify, recruit, consent and enroll persons with lung cancer (newly diagnosed or recent recurrence of disease) and their caregivers. Recruitment will continue until 25 patients and 25 caregivers (Case Dyads) are enrolled. Electronic health records for patients (appointment, clinical, and patient-reported data such as the M.D. Anderson Symptom Inventory that is standard of care) and study questionnaires will be used to evaluate quality and performance indicators. Questionnaires will be fielded with Case Dyads, as hereinafter defined, at baseline and after 8 weeks of exposure to FCA. Pre-post changes will be evaluated among cases.

### 3.3 Specific Aim 3

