***Observe quality and performance indicators among usual oncology care in similar patient-caregiver population to compare with cases.*** From non-treatment sites, identify, recruit, consent, and enroll persons with lung cancer (newly diagnosed or recent recurrence of disease) and their caregivers into the evaluation study. Recruitment will continue until 25 patients and 25 caregivers are enrolled (Control Dyads). Electronic health records for patients (appointment, clinical, and patient-reported data such as the M.D. Anderson Symptom Inventory that is standard of care) and study questionnaires will be used to evaluate quality and performance indicators however, questionnaires will be fielded at the post-period only. Non-treatment sites will not provide FCA as standard of care and function as control sites. These sites will include Geisinger Wyoming Valley in Wilkes-Barre, PA (“GWV”), and Geisinger Community Medical Center in Scranton, PA (“GCMC”). A case-matched controlled design will be used to evaluate differences in quality and performance indicators between groups at the post-period only.

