#### **4.2.1 Approximate Number of Subjects**

Approximately 135 Geisinger subjects (65 patients and 50 caregivers) will participate in the study. Patients are able to participate independent of having a caregiver; therefore the number of Geisinger patients enrolled is reflective of this possibility. Our goal is to include 100 participants in our analysis (50 patients and 50 caregivers) organized as 25 Cases Dyads and 25 Control Dyads. We will enroll 20 Geisinger providers in the treatment site who will participate in this study. If a caregiver receives care at Geisinger, his/her patient-related records are not of interest to or related to this study.

Background Logic Regarding Sample Size: The number of eligible lung cancer patients was estimated from a twelve-month report (May 2016-April 2017) ("Estimate Time Period") from each respective hospital which informed the Exploratory Evaluation Study design. Patients were included if, during the Estimate Time Period, they had an active lung cancer diagnosis on the EHR problem list and had an encounter at one of the following oncology departments (Hematology Oncology Danville, Radiation Oncology Danville, Hematology Oncology GWV, Radiation Oncology GWV) ("Inclusion Criteria"). There were 153 eligible patients from GMC ("GMC Lung Cancer Patients"), 137 eligible patients from GWV ("GWV Lung Cancer Patients"), and 21 eligible patients from GCMC ("GCMC Lung Cancer Patients") for potential inclusion in the Exploratory Evaluation Study and Phase III FCA expansion rollout. Given that the Exploratory Evaluation Study period is 6 months, the estimated count of eligible patients is reduced by 50% to 77 Case patients at GMC, 69 Control patients at GWV and 11 Control patients at GCMC.

Based upon Phase II enrollment at GMC, it is anticipated that 37% of eligible GMC Lung Cancer Patients (i.e., 28) will consent to participate in the evaluation and enroll as a Dyad. Based on Phase II enrollment at GMC, 100% of these patients will identify a caregiver who consents to

*Version 1.10 – 5.24.2018*

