participate as part of a dyad. Based on Phase II observations, 90% of these Dyads (i.e., 25) will complete an intensive 8-week treatment cycle. Recognizing variability in the incidence of disease, we chose the more conservative sample size of 25 patients enrolling in the study as part of a dyad for each arm thus resulting in 25 Case Dyads and 25 Control Dyads or 100 patient-caregiver participants. Based on Phase II observations, 90% are estimated to complete the 8-week treatment cycle and study.

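### Section 4.8.2 gives 50 Case and 50 Control Dyads, twice the 25 and 25 set everywhere else and more than the planned 65 patients and 50 caregivers can form

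*Combined protocol and SAP*

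**What the plan says.** Section 4.8.2 states that neither power nor sample size was estimated, and then that "a sample size of 50 Case Dyads and 50 Control Dyads was selected to describe any differences in quality and performance metrics". It adds that any tests are descriptive.

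The other sections that give a dyad target say 25 per group:

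- Section 3.2 (Aim 2), cases: "Recruitment will continue until 25 patients and 25 caregivers (Case Dyads) are enrolled".
- Section 3.3 (Aim 3), controls: "Recruitment will continue until 25 patients and 25 caregivers are enrolled (Control Dyads").
- Section 4.2.1, which holds the sample size reasoning: "we chose the more conservative sample size of 25 patients enrolling in the study as part of a dyad for each arm".
- Section 4.3: replacement dyads are sought with 25 as the enrolment goal in each group.
- Section 4.4.2: an analysis goal of 100 people, arranged as 25 dyads per group.

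On head count, section 4.2.1 says "Approximately 135 Geisinger subjects (65 patients and 50 caregivers) will participate in the study", and section 4.4.2 gives 115 people with the same split of 65 and 50. Sections 4.6 and 4.8.1 average the patient and caregiver scores within each dyad and compare these means between groups.

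**The concern.** The section a reader consults for the sample size carries a figure that no other part of the plan supports. In a powered trial the error would reach the power statement. Here there is none, so what is at stake is how the plan and its results are read. A statistician, ethics board or journal reviewer relying on 4.8.2 would expect twice as many units in the primary comparison, and correspondingly narrower intervals. A study that met its real target of 25 + 25 would also appear to have reached only half of its stated size.

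**Working it through.** **1. The plan's own derivation (4.2.1).**

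- Inputs: 153 eligible patients in twelve months at GMC, 137 at GWV and 21 at GCMC, halved for a six-month period ("reduced by 50% to 77 Case patients at GMC, 69 Control patients at GWV and 11 Control patients at GCMC"); consent ("it is anticipated that 37% of eligible GMC Lung Cancer Patients (i.e., 28) will consent to participate in the evaluation"); completion ("90% of these Dyads (i.e., 25) will complete an intensive 8-week treatment cycle").
- Eligible at GMC: 153 × 0.5 = 76.5, stated as 77.
- Consenting as dyads: 77 × 0.37 = 28.5, stated as 28.
- Completing: 28 × 0.90 = 25.2, stated as 25.

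The chain reproduces 25 per group. It does not give 50.

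**2. What 50 per group would require.**

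- GMC: 50 / 77 = 65% consent, against the 37% anticipated.
- Control sites: 69 + 11 = 80 eligible, so 50 / 80 = 62.5%. The plan gives no consent rate for these sites. If the GMC rate held there, and ignoring losses to 1:1 matching, they would yield 80 × 0.37 = 29.6 dyads. This is an assumption, and the conclusion does not depend on it.

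**3. Head count.** A dyad is one patient plus one caregiver.

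| | Dyads in total | Patients needed | Caregivers needed |
|---|---|---|---|
| Section 4.8.2 | 50 + 50 = 100 | 100 | 100 |
| Other sections | 25 + 25 = 50 | 50 | 50 |
| Planned enrolment | at most min(65, 50) = 50 | 65 available | 50 available |

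For 4.8.2 the plan is short by 100 − 65 = 35 patients and 100 − 50 = 50 caregivers. The total of 135 in 4.2.1 leaves no room for more dyads: 65 + 50 = 115, and the 20 providers bring it to 135.

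**4. Illustration of precision.** The plan gives no SD and no precision target. For an unpaired difference in mean dyad scores, in SD units, the 95% half-width is t(0.975, 2n − 2) × √(2/n):

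- n = 50 per group: 0.397
- n = 25 per group: 0.569

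The ratio is 0.569 / 0.397 = 1.43. Normal quantiles give 0.392 and 0.554, with the same message.

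**5. Completion (bears only on the optional clarification).** 25 × 0.90 = 22.5, so about 22 to 23 dyads per group would have post-period surveys, or 22.5 × 2 groups × 2 people = 90 people. The half-width is 0.594 at n = 23 and 0.608 at n = 22.

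**The case against.** The strongest reply is that little depends on the figure. Section 4.8.2 disclaims any power or sample size estimate, and 4.8.1 calls all tests descriptive. The points at which recruitment stops (3.2, 3.3) and the replacement goals (4.3) are unambiguous at 25, and 4.2.1 sets out a complete derivation of that number. The 50 may simply be a mislabel for 50 people per group or 50 dyads in total, although the documents do not say so. The precision figures are this review's illustration. They assume an unpaired comparison of means, while 4.8.1 also allows chi-square and non-parametric tests and the controls are matched 1:1. All of this stands and limits the weight of the point. None of it makes 4.8.2 correct.

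Two stronger readings are tempting, and the documents do not support them.

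- A reader might infer that a power claim fails or that recruitment will miss its target. There is no power claim, and recruitment works to 25.
- A reader might infer that the analysis goal of 100 people contradicts the 90% completion rate, because 25 enrolled per group leaves about 22 to 23. It does not. Sections 4.2.1 and 4.4.2 state a goal, 4.2.1 discloses the 90%, and the analysis also uses health record and application usage data. A dyad without a post-period survey can contribute to those. What is left is an ambiguity over whether 25 means enrolled or surveyed.

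**Conclusion.** The point holds as an internal contradiction. Section 4.8.2 states 100 dyads where the rest of the plan states 50, an overstatement by a factor of 2, and planned enrolment cannot form the larger number. This conclusion rests only on counts in the documents. The effect on apparent precision, about 0.57 SD against 0.40 SD, rests further on an unpaired comparison of means. The error affects how the plan and its results are read, not how the study is run. It should be corrected, but it invalidates no analysis.

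**What to change.** In section 4.8.2, change 50 to 25 for both the Case Dyads and the Control Dyads. This is a wording change in one sentence. Recruitment, matching, the caregiver total and the analysis stay as they are.

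Optionally, and not as the correction of an error, the sponsor could state in 4.2.1 and 4.4.2 whether 25 per group means dyads enrolled or dyads with post-period surveys. If it means enrolled, one added sentence would tell the reader to expect about 22 to 23 dyads per group in the post-survey comparison at the plan's own completion rate. If it means surveyed, about 25 / 0.90 = 28 dyads per group would have to enrol, and the planned 50 caregivers would have to rise to about 56. The documents do not settle which is intended, so that choice is the sponsor's.

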### **4.9 Data Management**

#### **4.9.1 Data Collection and Storage**

Each patient, caregiver, and provider will be assigned a unique study ID number by the data broker that will enable linkage of data from different data sources. The study ID number will be used to track their participation in the surveys and to link the patient, caregiver, and provider FCA usage, demographics, and EHR data.

Electronic informed consent and study surveys will be administered using a user-friendly, HIPAA compliant package that supports secure online data collection, REDCap. Hard copy surveys and informed consents will be entered and tracking in REDCap. All data will be stored within secure Geisinger databases and that password protected on secure network servers. Any hard copy study data will be stored in a locked filing cabinet in a locked office.

Aggregate reports will be shared with Merck to provide updates on recruitment and outcomes related to the evaluation (Milestones 5-7: Progress Report for Enrollment of Exploratory Evaluation Study Dyads) as well as study finding as part of the Exploratory Evaluation (Milestones 8-10: Exploratory Evaluation Study Reports). All reports will be sent via e-secure. All analysis will occur at Geisinger and no data sets will be shared with Merck.

While this project is sponsored by Merck, there are no Merck medications or devices used in the project and we do not anticipate hearing about a Merck product from any participant. However, *Version 1.10 – 5.24.2018*

consistent with the sponsor's request, we've agreed to anonymously report adverse events related to Merck products that might be "collected" via the project. For instance, a participant (patient) may offer an unsolicited comment to a research assistant about a Merck product or there may be a free text comment in FCA that specifically names a Merck product. No PHI would be shared with Merck. Merck will provide adverse event training to the study staff. See **Appendix A** for more details on the sponsors reporting requirements and administrative and regulatory details.

#### **4.9.2 Records Retention**

At the completion of the study, data generated as part of the study will be retained for 6 years in accordance with Geisinger policy. At the end of that 6-year period the data set will be available for use for future studies as approved by GHS IRB.

### **5 PROTECTION OF HUMAN SUBJECTS**

#### **5.1 Informed Consent**

We are asking for a waiver of consent/authorization for recruitment purposes. This study involves no more than minimal risk and will not affect the rights and welfare of the patients or providers. The recruitment and research could not be conducted without a waiver of consent because passive recruitment strategies typically yield low rates of recruitment, and this study is being conducted in a targeted population of patients and providers.

Dyads (patients and caregivers) who meet inclusion criteria will be approached and will provide informed consent (eConsent OR paper) to participate in the study.

We request a waiver of documentation of consent with an alteration of the consent to not include all elements of the consent for provider interviews. Providers will provide implied consent by agreeing to participate in the interview.

#### **5.2 Protection of Human Subjects Against Risks**

For participating patients, caregivers, and providers, there are minimal risks involved.

A participant's decision regarding participation in this study will not affect their care, access to care or employment. While there is always a risk of loss of privacy and confidentiality, the study team will do the following to make sure risks remain minimal:

- All data will be stored on password-protected computers
- All paper copies will be kept in a locked office or locked filing cabinet
- Unique study ID's will be used to link patient, caregiver, and provider information.
- Geisinger will retain the document linking the study ID back to the patient MRN.

#### **5.3 Data Monitoring Plan**

Data will not be shared outside of Geisinger.

Any problematic clinical issues that arise as part of the study will be reported immediately to the study investigators and oncology leadership. The issues will be reviewed as a group and addressed as soon as possible. All clinical issues and resolutions will be documented.

## **6 PUBLICATION PLAN**

Results of this project will be used to create manuscripts for publication, abstracts for submission to appropriate national conferences, and reports to the study sponsor. All information shared will be aggregate with no possibility of identifying participants from information provided. Geisinger will submit to Office of Scientific and Technical Clearance (OSTIC) for review prior to submission of any abstracts or publications.

## 8 ATTACHMENTS

- Attachment A: Pre-Treatment Survey: Patient
- Attachment B: Pre-Treatment Survey: Caregiver
- Attachment C: Post-Treatment Survey: Patient
- Attachment D: Post-Treatment Survey: Caregiver
- Attachment E: Informed Consent – Case
- Attachment F: Informed Consent – Control
- Attachment G: Initial Recruitment Email Caregiver – Case
- Attachment H: Reminder - Pre-Treatment Caregiver Communication – Case
- Attachment I: Initial Post- Treatment Patient Communication- Case
- Attachment J: Initial Post- Treatment Caregiver Communication- Case
- Attachment K: Reminder - Post-Treatment Patient Communication – Case
- Attachment L: Reminder - Post-Treatment Caregiver Communication – Case
- Attachment M: Initial Recruitment Email Caregiver- Control
- Attachment N: Reminder - Recruitment Email Caregiver- Control
- Attachment O: Initial Post-Treatment Survey Patient Communication- Control
- Attachment P: Initial Post-Treatment Survey Caregiver Communication- Control
- Attachment Q: Reminder - Post-Treatment Survey Patient Communication – Control
- Attachment R: Reminder - Post-Treatment Survey Caregiver Communication – Control
- Attachment S: Remote Caregiver Letter
- Attachment T: Compensation Letter
- Attachment U: RA Talking Points
- Attachment V: RA Scripts
- Attachment W: Recruitment Flyer – Cases
- Attachment X: Recruitment Flyer – Controls
- Attachment Y: Physician Interview Guide
- Attachment Z: Non-Participant Survey
- Attachment AA: Provider Interview Email Invitation
- Attachment BB: Consent Form Copy Letter
